### 15. Health Economics

#### 15.1. Aim

The economic component will analyse the costs and outcomes associated with desogestrel treatment, in comparison to the COCP, for people with problem bleeding whilst using the implant. If treatment with desogestrel is non-inferior to the COCP, there could still be important cost implications for the healthcare sector. The primary base case analysis will therefore adopt a NHS/PSS (Personal Social Services) perspective in line with NICE guidelines [25].

### 15.2. Outcome measurement

The primary outcome for the trial will be as described in Section 2 in terms of the non-inferiority of desogestrel to the COCP in treating problem bleeding during a 90-day reference period for people with problem bleeding whilst using the etonogestrel implant. We will use the data collected within the trial, so estimates of costs and benefits will relate to the initial 90-day period. Alongside the clinical outcomes collected in the trial and in line with recommendations from NICE, data will also be captured that will allow QALYs to be used as an outcome measure in the cost-effectiveness analysis [25, 26]. It is recommended that QALYs are calculated so that cost-effectiveness can be compared across disease areas. This will require changes in health-related quality of life (HRQL) to be captured for both trial arms. NICE recommends the use of EQ-5D-5L to measure HRQL. We will explore broader impacts on wellbeing as additional analyses using the ICECAP-A instrument. The ICECAP-A instrument has been widely used in a range of health areas, particularly where impacts on patients are anticipated to be broader than health alone [27]. These questionnaires will be administered to compare changes in health-related quality of life and wellbeing for the two trial arms, at baseline and at 30, 60 and 90 days.

### 15.3. Resource Use Measurement

Resource use data will be prospectively collected to estimate the costs associated with both desogestrel and COCP alongside the etonogestrel implant. The main resources to be monitored include:

1. The costs associated with treatment (provision of desogestrel and COCP)
2. Time and resource use incurred in SRH settings associated with clinical examination, additional treatments and monitoring during the follow up period and to treat any adverse events
3. Costs associated with discontinuation of the implant
4. Costs associated with GP attendances, A&E visits and other NHS secondary care.
5. Any other health and social care resource use

Costs such as those incurred by implant users and their families (e.g. associated with problem bleeding), will also be captured to allow a societal perspective to be explored as a secondary analysis. Information on unit costs or prices will be sourced to attach to each resource use item, to enable an overall cost per participant to be calculated (e.g. Unit Costs of Health and Social Care [28] and NHS Reference Costs [29]).

### 15.4. Analysis

The initial economic analysis will assess cost-effectiveness based on participant self-reported significant improvement in the bleeding pattern, reflecting the primary clinical outcome of the trial. A secondary analysis of incremental cost per QALY gained will also be undertaken in line with NICE recommendations. The economic evaluation will be conducted and reported in accordance with relevant guidelines [30, 31]. Initially, the base-case analysis will be framed in terms of cost-consequences, reporting data in a disaggregated manner on the incremental cost and the important consequences as assessed in the trial. An incremental economic analysis will then be conducted. Results will be presented using cost-effectiveness acceptability curves (CEACs) to show the uncertainty surrounding the cost-effectiveness of the intervention [32]. We shall also use both simple and probabilistic sensitivity analyses to explore the robustness of these results to plausible variations in key assumptions, especially around the costs associated with discontinuation and variations in the analytical methods used, and to consider the broader issue of the generalisability of the results [33].

## 16. Trial Organisational Structure

### 16.1. Sponsor

The University of Nottingham will be the sponsor of the DEBI trial. The role and responsibilities of the Sponsor are outlined in the current version of the trial Delegation of Responsibilities (DoR).

### 16.2. Trials Unit

The trial is co-ordinated by the Nottingham Clinical Trials Unit (NCTU). The role and responsibilities of the Trials Unit are outlined in the current version of the trial Delegation of Responsibilities (DoR).

### 16.3. Trial Management Group

The TMG includes those individuals responsible for the day-to-day management of the trial, such as the Chief Investigator, Statistician, Trial Manager, Data Manager, with other members of the trial team attending as required. The role of the group is to ensure high quality trial conduct, to time and within budget, to monitor all aspects of the conduct and progress of the trial, ensure that the protocol is adhered to and take appropriate action to safeguard participants and the quality of the trial itself. The TMG will report to the Independent Trial Steering Committee (TSC). The role of the TMG is outlined in the current version of the trial TMG terms of reference.

### 16.4. Trial Steering Committee

The role of the TSC is to provide overall supervision for the trial on behalf of the Sponsor and Funder and to ensure that the trial is conducted to the rigorous standards set out in the Department of Health's UK Policy Framework for Health and Social Care Research and the Guidelines for Good Clinical Practice. The TSC monitors trial progress and conduct. The TSC will consider and act, as appropriate, upon the recommendations of the DMC or equivalent and ultimately carries the responsibility for deciding whether a trial needs to be modified or stopped on grounds of safety or efficacy.

The TSC includes members who are independent of the Investigators, their employing organisations, funder and Sponsor. The TSC will operate in accordance with a trial specific charter. The TSC will meet annually at a minimum but more frequently as requested by the committee, dependent on trial activity or phase. More information on the TSC can be found in the current version of the trial TSC charter.

### 16.5. Data Monitoring Committee

The role of the DMC is to monitor the unblinded trial data and make recommendations to the TSC on whether there are any ethical or safety reasons why the trial should stop, or aspects of the trial design be amended. This is to safeguard the interest of the participants, investigators and Sponsor. Members of the DMC are independent of the trial (i.e. should not be involved with the trial in any other way or have any competing interest that could impact on the trial).

Reports will be supplied in confidence to an independent DMC, which will be asked to give advice on whether the accumulated data from the trial, together with the results from other relevant research, justifies the continuing recruitment of further participants. The DMC will operate in accordance with a trial specific charter based upon the template created by the Damocles Group. The DMC will meet annually at a minimum but more frequently as requested by the committee, dependent on trial activity or phase.

Additional meetings may be called if recruitment is much faster than anticipated and the DMC may, at their discretion, request to meet more frequently or continue to meet following completion of recruitment. An emergency meeting may also be convened if a safety issue is identified. The DMC will report directly to the Trial Steering Committee (TSC) who will convey the findings of the DMC to Trial Steering Committee, funders, and Sponsors as applicable. More information on the DMC can be found in the current version of the trial DMC charter.

### 16.6. Finance

This trial is funded by the National Institute for Health Research Health Technology Assessment Programme, award ID: NIHR153258.

### 16.7. Participant gratitude and stipends

Participants will not receive payment to participate in the DEBI trial. Participants will be offered shopping vouchers to encourage responses to the trial questionnaires at 30-, 60- and 90-days post randomisation. On receipt of the completed questionnaires participants will receive a £15 gift voucher as a thank you for the time spent completing the questionnaires (3 x £15 = maximum total of £45 across the trial duration).

### 17. Ethical Considerations

The trial will be performed in accordance with the recommendations guiding physicians in biomedical research involving human participants, adopted by the 18th World Medical Association General Assembly, Helsinki, Finland, June 1964, amended at the 48th World Medical Association General Assembly, Somerset West, Republic of South Africa, October 1996 (website: [Declaration of Helsinki 1996 – WMA – The World Medical Association](#)).

The trial will be conducted in accordance with the UK Policy Framework for Health and Social Care Research, 2017, the applicable UK Statutory Instruments, (which include the Medicines for Human Use (Clinical Trials) Regulations, 2004 and subsequent amendments and the Data Protection Act 2018) and Guidelines for Good Clinical Practice (GCP). This trial will be carried out under a Clinical Trial Authorisation in accordance with the Medicines for Human Use (Clinical Trials) Regulations, 2004. The protocol will be submitted to and approved by the REC prior to circulation.

### 18. Confidentiality and Data Protection

Personal data recorded on all documents will be regarded as strictly confidential and will be handled and stored in accordance with the Data Protection Act 2018.

Participants will always be identified using only their unique trial identification number on the CRF and correspondence between NCTU and the participating site. Participants will give their explicit consent for the movement of their consent form, giving permission for the NCTU to be sent a copy. This will be used to perform in-house monitoring of the consent process.

The Investigator must maintain documents not for submission to NCTU (e.g. Participant Identification Logs) in strict confidence. In the case of specific issues and/or queries from the regulatory authorities, it will be necessary to have access to the complete trial records, provided that participant confidentiality is protected.

NCTU will maintain the confidentiality of all participant's data and will not disclose information by which participants may be identified to any third party other than those directly involved in the

treatment of the participant and organisations for which the participant has given explicit consent for data transfer (e.g. Registries, laboratory staff, competent authority, Sponsor). Representatives of the DEBI trial, NCTU and Sponsor may be required to have access to participant's notes for quality assurance purposes but participants should be reassured that their confidentiality will be respected at all times.

### 19. Insurance and Indemnity

The University of Nottingham will act as sponsor for the trial. Delegated responsibilities will be assigned to the NHS Trusts taking part and NCTU. Third party suppliers, such as IPS Pharma will be contracted by NCTU. Insurance and indemnity for trial participants and NHS trial staff is covered within the NHS Indemnity Arrangements for clinical negligence claims in the NHS, issued under cover of Health and Safety Guidance HSG (96) 48. There are no special compensation arrangements, but trial participants may have recourse to the NHS complaints procedure.

The University of Nottingham has appropriate and typical insurance coverage in place (including, but not limited to Clinical Trials, Professional Indemnity, Employer's Liability and Public Liability policies) in relation to the Institution's Legal Liabilities arising from the University's activities and those of its staff, whilst conducting University business and research activity. The University of Nottingham as research Sponsor indemnifies its staff with both public liability insurance and clinical trials insurance in respect of claims made by research subjects.

The University of Nottingham is independent of any pharmaceutical company, and as such it is not covered by the Association of the British Pharmaceutical Industry (ABPI) guidelines for participant compensation.

### 20. Publication Policy

The dissemination of the DEBI trial results will be via publication in the NIHR Journals Library (threaded publication) and submitted for publication in a peer reviewed journal. The manuscripts will be prepared by the Chief Investigator and TMG and authorship will be determined by mutual agreement.

Any secondary publications and presentations prepared by Investigators must be reviewed by the Chief Investigator or delegate and NCTU. Manuscripts must be submitted to both parties in a timely fashion and in advance of being submitted for publication, to allow time for review and resolution of any outstanding issues. Authors must acknowledge that the trial was performed with the support of the University of Nottingham.

During the trial, press releases may be issues from the Sponsor or NCTU. Presentations or other material prepared by local investigators to publicise the trial must be reviewed by the Chief Investigator or delegate and NCTU. No party will be entitled to submit any publicity material without prior approval of the NCTU.

Trial results presented in a plain English summary which will be sent to the participants via their preferred communication method. Results will be presented in different medias (e.g. infographics or videos) to improve accessibility of the findings. The findings will be disseminated among people via our PPI groups (including groups such as Reproductive Justice Initiative and CERT) and social media.

Sites will be invited to a results meeting where the findings of the trial will be shared prior to publication.

## 22. Appendices

### 22.1. Table 12 Concomitant medications

**Table 12-Concomitant medications**

Medication	Exclude from recruitment	Allow use during the trial	Action if used during the trial
Progestogens other than etonogestrel implant	Yes if used within 3 months prior to recruitment	No	Withdraw from trial, use data up to withdrawal
Estrogens within 3 months prior to recruitment	Yes	No	Withdraw from trial, use data up to withdrawal
Testosterone use within 3 months prior to recruitment	Yes	No	Withdraw from trial, use data up to withdrawal
Gonadotropin-releasing hormone (GnRH) analogues within 6 months prior to recruitment	Yes	No	Withdraw from trial, use data up to withdrawal
NSAIDs/mefenamic acid within 7 days of recruitment except Piroxicam use within 11 days	Yes	No	Do not withdraw. Record all use of NSAIDs/mefenamic acid for inclusion in the analysis
Tranexamic acid within 7 days prior to recruitment	Yes	No	Do not withdraw. Record all use of tranexamic acid for inclusion in the analysis
GLP-1 agonists (e.g. tirzepatide, semaglutide, exenatide, liraglutide, dulaglutide, lixisenatide) use within 3 months of recruitment	Yes	No	Withdraw from trial, use data up to withdrawal
Anticoagulants (e.g. warfarin, Low Molecular Weight Heparin {LMWH}, heparin or Direct Oral Anticoagulants {DOACs}) within 3 months of recruitment	Yes	No	Do not withdraw. Record all use of anticoagulants for inclusion in the analysis
Tamoxifen within 6 weeks of recruitment	Yes	No	Withdraw from trial, use data up to withdrawal

Ulipristal acetate within 6 weeks of trial	Yes	No	Withdraw from trial, use data up to withdrawal
Tetracycline antibiotics within 28 days prior to recruitment	Yes	No	Do not withdraw. Record all use of tetracycline antibiotics for inclusion in the analysis
Any use of CYP450 inducers within 6 weeks of trial recruitment 
 
• Anticonvulsants: phenytoin, fosphenytoin, primidone, rufinamide, carbamazepine, eslicarbazepine, oxcarbazepine, phenobarbitone, cenobamate, topiramate, lamotrigine
 
• Antibiotics: Rifampicin, rifabutin
 
• Antifungals: griseofulvin
 
• Systemic glucocorticosteroids: prednisolone, dexamethasone, hydrocortisone.
 
• Antiretrovirals: efavirenz , ritonavir
 
• Immunosuppressants : tacrolimus
 
• Other: St John’s wort, modafinil, bosentan, aprepitant, lumacaftor, statins
 
	Yes	No	Do not withdraw. Record all use of CYP450 inducers for inclusion in the analysis

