### 6.4.1. Emergency unblinding

In order to protect the safety and well-being of the participants during a medical emergency, unblinding will be performed within the REDCap trial database. Emergency unblinding will be performed by a member of the participants research team via REDCap. Unblinding via REDCap will be available and readily accessible at time of need. The use of REDCap, an electronic platform will ensure they are kept securely but accessible (including remotely) if required with full audit trail recorded. This process will be used to unblind the participant during the emergency, where knowledge of DEBI treatment is absolutely essential for further management.

The NCTU and CI will be notified automatically by email that the blind has been broken but will not be made aware of the participant’s allocation. The NCTU will notify the Sponsor as soon as possible after the event. Once notified, the NCTU should send the Emergency Unblinding Form to the site research team for completion. Once returned this should be reviewed by the Trial Manager (TM)/Senior Trial Manager (STM), PI, CI and Sponsor and the completed form filed in the Investigator Site File (ISF) and Trial Master File (TMF).

The decision to continue treatment for participants whose treatment allocation has been revealed will be decided by the recruiting site/participant clinical care team. The participant will remain in the trial unless they choose to withdraw.

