### 7.6. Dosing Schedules

Both trial treatments desogestrel 75mcg and COCP (levonorgestrel 150mcg/ethinylestradiol 30mcg) are to be taken orally, once a day, at the same time each day for the 90-day duration of a persons participation in the trial.

In the case of any missed doses, participants will be advised to take the dose as soon as they have remembered if less than 24 hours late. If a dose is more than 24 hours late the dose should be disregarded and the next dose taken. Participants will be asked to confirm they have taken their pill when they complete the daily bleeding diary. No participant will be removed from the trial for non-adherence to treatment schedule.

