**Table 8-Withdrawal type and procedure post randomisation**

Withdrawal type	Withdrawal procedure	Use of data
Withdrawal from trial treatment	Any participant that requests to discontinue trial treatment will be marked as withdrawn from treatment on the trial database but will be asked to continue to complete questionnaires if willing. Information on reason for stopping trial treatment will be recorded by the site if given, and patient care will continue as part of standard clinical practice.	Any data collected prior to participant withdrawal will be retained and used in the analysis.
Removal of implant	Any participant who notifies the trial or site team that their implant has been removed during their participation in the trial would be withdrawn from the trial and unblinded to their treatment allocation to	Any data collected prior to participant withdrawal will be retained and used in the analysis.

	inform their ongoing contraceptive care. Participants would not be required to complete any further questionnaires or daily diaries but would be followed up for safety outcomes for 7 days following stopping of their trial treatment.	
Withdrawal from daily bleed diary	Any participant that requests to discontinue from daily bleed diary will be marked as withdrawn from diary collection on the trial database and no further MyCap notifications will be sent. Withdrawal from the daily diary does not withdraw from questionnaire completion.	Any data collected prior to participant withdrawal will be retained and used in the analysis.
Withdrawal from follow up questionnaires	Any participant that requests to discontinue from trial questionnaires will be marked as withdrawn from questionnaire collection on the trial database and no further contact relating to questionnaires will be made. Withdrawal from questionnaires does not withdraw from daily diary completion.	Any data collected prior to participant withdrawal will be retained and used in the analysis.
Withdrawal from long-term follow-up	Any participant that withdraws consent for the long term follow-up will be recorded within the database and no long term follow-up data will be collected.	Any data collected prior to participant withdrawal will be retained and used in the analysis.

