### 14.3. Analysis of Outcome Measures

The reporting of the trial will be in accordance with the CONSORT extension to reporting of non-inferiority and equivalence randomised trials [24]. Full details of the statistical analysis will be provided in the Statistical Analysis Plan, which will be finalised and approved by the Trial Steering Committee (TSC) prior to database lock.

Comparative analysis will be performed for the primary outcome on both the intention to treat (ITT) population and some version of the per-protocol (PP) population (preferably complier average causal effect (CACE) analysis, if feasible/identified), as a protection against the ITT's possible increased risk of falsely claiming noninferiority (type I error). Primary estimand will be the treatment policy estimand (i.e., ITT population- analysing data on all randomised participants according to the randomised groups irrespective of subsequent compliance with the treatment allocation) with CACE (or per-protocol) results used to check the consistency. Full definition and cut-off for compliance will be specified in the Statistical Analysis Plan (SAP).

For the primary outcome, a two-sided 95% confidence interval for the between-group difference in proportion of participants reporting significant improvement will be constructed by fitting a mixed-effect logistic regression model, adjusting for site as a random effect and other minimisation factors as fixed effects. The model will include outcome data from all the 3 timepoints (30, 60, and 90 days) and will include treatment by time interaction to obtain the treatment effect at each timepoint with 90 days as the primary contrast. Estimates of model-adjusted difference in proportions and 95% confidence intervals will be obtained by contrasts of average marginal predictions in the fitted model. Non-inferiority of desogestrel will be inferred if the lower bound of this interval lies within the non-inferiority margin of 10%. Missing data for primary outcome will be dealt with through maximum likelihood estimation using mixed-effect model which will use all available follow-up data. Intercurrent events such as discontinuation of assigned treatment or treatment switching, if any, will be dealt with through treatment policy strategy for the primary analysis.

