#### 14.4.4. Procedures for missing, unused and spurious data

Every effort will be made to follow up all participants up to the primary endpoint, however, as missing data is inevitable, we will employ statistical techniques for handling missing data for the primary outcomes under the Missing At Random assumption such as further adjustment in the mixed model for variables predictive of missingness. For the primary analysis, only minimisation variables will be adjusted for as covariates and we do not expect any to be missing as they are required for the participant to be allocated.

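### Table 12 withdraws participants from the trial when they start another progestogen, an estrogen or ulipristal, which most naturally ends the questionnaires that the treatment-policy estimand needs at day 90

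*Protocol*

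**What the plan says.** Section 14.3 makes treatment policy the primary estimand and day 90 the primary contrast. On intercurrent events it says: "Intercurrent events such as discontinuation of assigned treatment or treatment switching, if any, will be dealt with through treatment policy strategy" for the primary analysis. Missing primary outcomes are left to maximum likelihood in the mixed model. Section 14.4.4 adds: "Every effort will be made to follow up all participants up to the primary endpoint".

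Table 12 (section 22.1) lists what to do when a prohibited medicine is used during the trial. Seven rows carry the action "Withdraw from trial, use data up to withdrawal": other progestogens, estrogens, testosterone, GnRH analogues, GLP-1 agonists, tamoxifen and ulipristal. Five rows (NSAIDs, tranexamic acid, anticoagulants, tetracyclines, CYP450 inducers) keep the participant in, for example: "Do not withdraw. Record all use of tranexamic acid for inclusion in the analysis".

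Table 8 (section 8.4.2) defines the kinds of withdrawal. In withdrawal from trial treatment, participants "will be asked to continue to complete questionnaires if willing". In the implant-removal row the participant is withdrawn from the trial as a whole, and there: "Participants would not be required to complete any further questionnaires or daily diaries".

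**The concern.** A treatment-policy estimand at day 90 is defined by the day-90 outcome whatever happened before, so that outcome has to be collected after a switch. If a switch ends follow-up, the model predicts day 90 from the answers given before it, under missing at random. That is closer to a hypothetical estimand in which nobody switches.

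Progestogens, estrogens and ulipristal are the switches one would expect here. COCP, itself an estrogen and a progestogen, is the first-line treatment in the UK guideline (section 1). Desogestrel can be obtained from a pharmacist without a prescription (section 1.1). Section 14.1 draws on ulipristal data for this same bleeding problem. At stake is a mismatch between the declared estimand and the data, in a non-inferiority trial whose primary inference is ITT. Table 12 is a conduct instruction, so a later analysis plan cannot put it right.

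**Working it through.** **1. What withdrawal from the trial means.** Table 12 does not define it. Three features point to the end of questionnaires.
- The same table has a contrasting instruction for five drug classes, and the two must differ in effect.
- Table 8 has a status for stopping tablets while questionnaires continue, and Table 12 does not use it.
- The one Table 8 row that speaks of being withdrawn from the trial, implant removal, ends questionnaires and diaries.

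Elsewhere the protocol keeps people in. Section 7.6: "No participant will be removed from the trial for non-adherence to treatment schedule". Section 6.4.1, after emergency unblinding: "The participant will remain in the trial unless they choose to withdraw".

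**2. Who is affected.** Medications are asked at days 30 and 60 (section 8.2.10), new medicines are self-reported (section 7.9), and repeated missed doses prompt a call to find the reason (section 7.11). A switch can therefore be known before day 90. Someone who first reports it on the day-90 form gives the primary answer on that form, and nothing is lost.

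**3. The plan's own figure.** Farrington-Manning, p = 0.85 in both arms, margin 0.10, one-sided 2.5%, power 90%. The restricted estimates are 0.787 and 0.887, so s0 = √(0.787×0.213 + 0.887×0.113) = 0.517, and s1 = √(2×0.85×0.15) = 0.505.

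n = [(1.960×0.517 + 1.2816×0.505)/0.10]² = 275.7, so 276 per arm. 552/0.80 = 690. Both figures reproduce.

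**4. Illustration of the bias.** All rates in this step are assumptions, because the protocol gives none. The truth is put on the margin (COCP 85%, desogestrel 75%), with 276 analysed per arm. P(conclude non-inferiority) = Φ{[(pD − pC + 0.10)√276 − 1.96·s0]/s1}, which is 2.5% with no switching. Let s be the proportion whose day-90 answer is lost and q the switchers' day-90 response.

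*Complete-case version*, for reference and not the planned analysis. The rate among those observed is (p − s·q)/(1 − s). With 2.5% lost on COCP, 5% on desogestrel and q = 0.2: COCP (0.85 − 0.005)/0.975 = 0.8667; desogestrel (0.75 − 0.010)/0.95 = 0.7789; difference −8.8 points; false non-inferiority 5.7%.

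*Approximation to the planned model.* A random-intercept logistic model with free means per arm and time and a common SD is fitted by maximum likelihood to expected response patterns. The true SD is 1, 2 or 3. Day 30/60 response is 60%/75% on COCP and 50%/62% on desogestrel. Switching is 5% on COCP and 10% on desogestrel. Half of it follows a day-30 non-response (days 60 and 90 lost) and half follows non-response at both days. The fitted day-90 rates go into the formula above.

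| q | Model, late switchers' day-90 answers kept (2.5%/5% lost), SD 1 to 3 | Model, all switchers' answers lost (5%/10%), SD 1 to 3 | Complete-case, 2.5%/5% lost | Complete-case, 5%/10% lost |
|---|---|---|---|---|
| 0.20 | 4.9% to 4.0% | 10.0% to 5.7% | 5.7% | 13.9% |
| 0.40 | 3.4% to 2.7% | 4.7% to 2.4% | 4.0% | 6.9% |
| 0.60 | 2.4% to 1.8% | 2.0% to 0.9% | 2.8% | 3.2% |
| 0.85 | 1.5% to 1.1% | 0.7% to 0.3% | 1.7% | 1.1% |

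In the first model column the shift in the estimated difference runs from +1.0 to −1.2 points. With equal 5% switching and late answers kept, the error is 1.9% to 2.1% at any q.

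With no true difference (85% in both arms, day 30/60 response 60%/75% in both) and q = 0.85, power is 88.8% to 84.7% with late answers kept and 84.9% to 70.0% with all lost, against 90.0% planned.

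**The case against.** The strongest reply is that the conflict is inferred. Table 12 never says questionnaires stop. The part of its instruction about using data up to withdrawal resembles Table 8's data column, which reads much the same in the row where questionnaires continue. Sites are trained to establish which activities a participant is leaving (section 8.4.2). Implant removal has its own reason for ending participation, namely unblinding for contraceptive care. This stands in part: a reader might infer that the protocol expressly ends follow-up after a switch, and it does not. But on the softer reading the text still misdirects sites, and the same rewording cures it.

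The scope is also narrower than seven rows suggest. Testosterone, GnRH analogues, GLP-1 agonists and tamoxifen are not clearly treatment switching. NSAIDs and tranexamic acid already stay in follow-up. The loss depends on someone acting before day 90, while follow-up is run mostly without the site (section 8.2.7) and participant-reported data are not queried (section 11.3). That half of switchers would lose their day-90 answer is an assumption.

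A reader might also infer that the rule inflates the false non-inferiority rate. The documents do not support that. Inflation needs more switching on desogestrel together with poor response in switchers. With equal switching, or an added hormone that works, the bias runs against desogestrel. With only 1% and 2% lost, even the complete-case error stays between 2.2% and 3.4%.

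**Conclusion.** The point holds as an inconsistency between a conduct rule and the declared estimand, and it should be fixed. Confidence is medium, because the meaning of the rule is inferred from Table 8 and from the contrast within Table 12. It bears on progestogens, estrogens and ulipristal, and on switches known before day 90. The other four withdraw rows matter for consistency only.

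The size and direction of the bias are unknown. Under the assumed 5%/10% switching with late answers kept, false non-inferiority lies between 1.1% and 4.9%. The wider figures need every switcher's answer to be lost, or an analysis that is not the planned one. The sample size is correct and is not in question. How outcomes after implant removal should be handled is a separate estimand choice, and nothing here shows that row to be wrong.

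**What to change.** In the progestogen, estrogen and ulipristal rows of Table 12, replace the action with: *Withdraw from trial treatment (Table 8); record the medicine and its dates for inclusion in the analysis; day 30/60/90 questionnaires and the diary continue unless the participant declines.* Use the same wording for testosterone, GnRH analogues, GLP-1 agonists and tamoxifen. Keep the treatment-policy primary analysis, and leave the implant-removal row of Table 8 as it is.

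Trial tablets still stop, so no safeguard is loosened. Leaving that decision to a blinded clinical team would be worse, since section 7.9 does not permit these hormones alongside trial treatment.

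The cost is a wording change that reuses an existing status and the remote follow-up already in place; 690 stays. The downside is some follow-up of participants off trial treatment who know what added medicine they take when they give a subjective answer. That comes with the treatment-policy strategy the sponsor chose.
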